9.5 SAMPLE SIZE DETERMINATION

There are no statistically powered hypotheses in this study thus no formal sample size computation. All analyses will be descriptive.

The sample size was set to approximatively 180 participants (minimum of 30 evaluable participants from the low - enrolling of the 2 priming vaccines) to have at least 150 evaluable participants assuming a drop-out rate of approximatively 15%.

In terms of immunogenicity for any of the 4 serogroups, considering a sample size of 150 evaluable subjects, the expected precision of the 95% CI using the Exact binomial method will be as follow:

Seroprotection rates (titer >= 1:8)	Precision*
85%	13.77
90%	11.62
95%	8.96
100%	2.88

^{*}Difference between the upper and lower bounds of the 95%CI

In terms of safety, the planned sample size will allow for identification of common AEs. One hundred and fifty evaluable subjects will allow with 95% probability, the detection of an AE occurring with a frequency of 2% or more, using the rule of threes.

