3.2 Sample Size Determination

There are no statistically powered hypotheses in this study thus no formal sample size computation. All analyses will be descriptive.

The sample size was set to approximatively 180 participants (minimum of 30 evaluable participants from the low-enrolling of the 2 priming vaccines) to have at least 150 evaluable participants assuming a drop-out rate of approximatively 15%.

In terms of immunogenicity for any of the 4 serogroups, considering a sample size of 150 evaluable participants, the expected precision of the 95% CI using the Exact binomial method will be as follow:

Seroprotection rates (titer >= 1:8)	Precision*
85%	13.77
90%	11.62
95%	8.96
100%	2.88

^{*}Difference between the upper and lower bounds of the 95%CI

In terms of safety, the planned sample size will allow for identification of common AEs. One hundred and fifty evaluable participants will allow with 95% probability, the detection of an AE occurring with a frequency of 2% or more, using the rule of threes.

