3.4 Statistical Analyses

3.4.1 General Considerations

Immunogenicity parameters will be analyzed in specified analysis sets (PPAS and FAS) in the overall population, as well as by primed vaccine groups. Safety analysis will be performed on the SafAS.

The statistical analyses will be performed under the responsibility of the Sponsor's Biostatistics platform using SAS® Version 9.4 or later.

For descriptive purposes, the following statistics will be presented:

Table 3.1: Descriptive statistics produced

Disposition and follow-	Categorical data	Number of participants.		
up description		Percentage of participants.		
	Continuous data	Mean, standard deviation, quartiles, minimum and		
		maximum.		
Baseline characteristics	Categorical data	Number of participants.		
		Percentage of participants.		
	Continuous data	Mean, standard deviation, quartiles, minimum and		
		maximum.		
Clinical safety results	Categorical data	Solicited: Number and percentage (95% CIs for		
		main endpoints) of participants.		
		Unsolicited: Number and percentage (95% CIs for		
		main endpoints) of participants and number of		
		events.		
Immunogenicity	Categorical data	Number and percentage (95% CIs for main		
results	(seroprotection,	endpoints) of participants		
	seroconversion, cutoff)			
	Continuous data (titer /	Log10: Mean and standard deviation. Anti-Log10		
	data†)	(work on Log10 distribution, and anti-Log10		
		applied): Geometric mean, 95% CI of the geometric		
		mean, quartiles, minimum, and maximum. Graphical		
		representation by Reverse Cumulative Distribution		
		Curve (RCDC).		

The confidence interval (CI) for the single proportion will be calculated using the exact binomial method (Clopper-Pearson method, quoted by Newcombe (1), i.e., using the inverse of the beta integral with SAS®.

For immunogenicity results, assuming that Log10 transformation of the titers / data follows a normal distribution, at first, the mean and the 95% CI will be calculated on Log10 (titers / data) using the usual calculation for normal distribution (using Student's t distribution with n-1 degree of freedom), then antilog transformations will be applied to the results of calculations, in order to provide geometric means (GMs) and their 95% CI.

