3.4.3 Safety Endpoints

Safety analyses will be performed on the SafAS and presented overall. The main parameters for the safety endpoints will be described by 95% CIs using the Exact binomial method (Clopper-Pearson method).

The safety analysis that will be presented by priming vaccines status for the following safety summary tables:

- Safety overview after MenACYW conjugate vaccine dose received at V01,
- Summary of unsolicited AEs within 30 days after MenACYW conjugate vaccine dose received at V01
- Overview of SAEs.

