4.2.5.4 Duration of the Study

The durations are computed in days as follows: Latest period date - Earliest period date + 1.

5 Changes in the Conduct of the Trial or Planned Analyses

Immunogenicity results by number of doses received in the priming schedule will not be described because we only have participants who had 2 priming doses of meningococcal quadrivalent vaccination.

The sample size was set to approximatively 180 participants (minimum of 30 evaluable participants from the low - enrolling of the 2 priming vaccines) to have at least 150 evaluable participants assuming a drop-out rate of approximatively 15%, however the recruitment had to be stopped before reaching 180 subjects in total (and minimum of 30 evaluable participants enrolling of the 2 priming vaccines), due to the low recruitment rate. Mitigation plan was set up and the recruitment period was extended but finally when no more improvement was possible it was decided in agreement with the principal investigator to stop the recruitment as the analysis are descriptive.

COVID FORM was not applied to the study as due to administrative issue study was pushed further and started only after COVID was no more of a Pandemic issue.

As per diary card structure both Evening temperature and Additional temperature are collected. The highest temperature will be used for statistical analysis.

6 Supporting Documentation

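### The precision table in SAP 3.2 and protocol 9.5 is labelled as 95% exact CI widths, but it holds 97.5% widths

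*SAP*

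**What the plan says.** SAP 3.2 states that there is no formal sample size computation and that all analyses are descriptive. It then describes what 150 evaluable participants would deliver: "considering a sample size of 150 evaluable participants, the expected precision of the 95% CI using the Exact binomial method" is tabulated for four seroprotection rates (hSBA titer of 1:8 or more).

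| Rate | Printed precision |
|---|---|
| 85% | 13.77 |
| 90% | 11.62 |
| 95% | 8.96 |
| 100% | 2.88 |

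A footnote defines precision as "Difference between the upper and lower bounds of the 95%CI". Protocol 9.5 introduces the identical table with "considering a sample size of 150 evaluable subjects, the expected precision of the 95% CI using the Exact binomial method". SAP 3.4.1 fixes the method for the analysis: "The confidence interval (CI) for the single proportion will be calculated using the exact binomial method", namely Clopper-Pearson through the inverse beta integral. Neither document mentions a 97.5% level.

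SAP 3.2 also says of safety: "One hundred and fifty evaluable participants will allow with 95% probability, the detection of an AE occurring with a frequency of 2% or more". SAP 5, which records changes, says that "the recruitment had to be stopped before reaching 180 subjects in total (and minimum of 30 evaluable participants enrolling of the 2 priming vaccines", because recruitment was slow. It gives no attained numbers. Immunogenicity is still to be shown "in the overall population, as well as by primed vaccine groups", and SAP 3.4.3 lists three safety tables by priming vaccine.

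**The concern.** The method, sample size, confidence level and definition of width are all stated, so the table should reproduce exactly. It does not. With no hypothesis and no power calculation, the table and the adverse event sentence are the only numbers in the section that tell a reader what 150 participants would give. A reader who checks the table, or uses it to plan a similar study, would be misled about the confidence level.

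A second, smaller matter is that SAP 3.2 keeps its n = 150 statements without a note, although SAP 5 of the same document reports an early stop to recruitment.

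**Working it through.** **Inputs.** n = 150 and rates of 85%, 90%, 95% and 100% (SAP 3.2, protocol 9.5). Width is upper minus lower limit (table footnote). The interval is two-sided Clopper-Pearson (SAP 3.4.1).

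**Formula.** For x responders out of n and two-sided error α:
- lower limit = Beta quantile at α/2 with parameters (x, n − x + 1)
- upper limit = Beta quantile at 1 − α/2 with parameters (x + 1, n − x), or 1 if x = n

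**Counts.** 150 × 0.85 = 127.5; 150 × 0.90 = 135; 150 × 0.95 = 142.5; 150 × 1.00 = 150. Rounded down: 127, 135, 142, 150.

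**Widths in percentage points.**

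| Rate | x | Printed | 95% (α = 0.05) | 97.5% (α = 0.025) | Printed minus 95% | Excess |
|---|---|---|---|---|---|---|
| 85% | 127 | 13.77 | 12.14 | 13.770 | 1.63 | 13% |
| 90% | 135 | 11.62 | 10.25 | 11.621 | 1.37 | 13% |
| 95% | 142 | 8.96 | 7.91 | 8.959 | 1.05 | 13% |
| 100% | 150 | 2.88 | 2.43 | 2.879 | 0.45 | 19% |

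The 97.5% column reproduces all four printed values to two decimals. The 95% column reproduces none.

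**Hand check on the 100% row.** With x = n the width is 1 − (α/2)^(1/n).
- α = 0.05: 1 − 0.025^(1/150) = 2.43 points
- α = 0.025: 1 − 0.0125^(1/150) = 2.88 points, the printed value

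**Could rounding explain it?** No. The 90% and 100% rows have whole-number counts and still differ. In the other two rows, rounding up (128 and 143) gives 95% widths of 11.93 and 7.48, and fractional counts give 12.04 and 7.70. All are further from the printed 13.77 and 8.96.

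**Could another n or method explain it?** No. At 95%, no n from 20 to 399 gives all four printed values, whether x is rounded down, rounded up or left fractional. At 97.5% with x rounded down, only n = 150 does. Wald, Wilson, Agresti-Coull and Jeffreys intervals at n = 150, at either level, do not reproduce the table. A plausible cause, which is an inference only, is that 0.025 was entered as α and then halved again.

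**Other figures in the section.** 150 / 0.85 = 176.5, so about 180 enrolled is consistent. 3/150 = 2% and 1 − 0.98^150 = 95.2%, so the adverse event sentence is right at 150.

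**How far could n fall before the printed widths fail at 95%?** With x rounded down, every n from 127 to 150 keeps all four true widths within the printed ones. At n = 127 (x = 107, 114, 120, 127) they are 13.38, 11.30, 8.78 and 2.86. At n = 126 the 100% row is 2.89, just above 2.88.

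**Adverse event detection.** Safety uses everyone vaccinated (the SafAS), so evaluable counts must not be carried over. At the documents' 15% drop-out, 127 evaluable corresponds to 127 / 0.85 ≈ 149 vaccinated, and 1 − 0.98^149 = 95.1%.

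**The case against.** The strongest case against giving this weight is that nothing depends on the table. The study is descriptive, the table describes what 150 gives rather than deriving 150, the analysis intervals are correctly specified in SAP 3.4.1, and the error makes the design look slightly less precise than it is. All of that stands. It limits the weight of the point but does not make the table correct.

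On the early stop, the objection largely succeeds. SAP 5 is the proper place for changes. It restates the 180, 150 and 30 targets in the past tense and gives the reason for stopping. Table 3.1 of the SAP provides for disposition counts and for 95% intervals on the main endpoints, so observed precision will be visible. Neither document ever stated a precision for a priming group.

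A reader might infer two stronger things, and the documents support neither.

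- **That the stated overall precision was lost.** No attained number is given. About 177 enrolled would yield 150 evaluable at 15% drop-out, so a stop somewhat below 180 is compatible with 150.
- **That adverse event detection in the smaller priming group was at best that of 29 children.** The SAP 5 sentence is garbled. Its natural reading is that the minimum of 30 evaluable was also missed, but even then 29 is a ceiling on evaluable participants, not on vaccinated ones. At 15% drop-out, 29 evaluable implies 29 / 0.85 ≈ 34 vaccinated. The chance of seeing a 2% event is then 1 − 0.98^34 ≈ 50%, against 44% if 29 is used.

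**Conclusion.** The table is wrong as labelled in both documents. Its values are 97.5% widths, and the 95% widths at n = 150 are 12.14, 10.25, 7.91 and 2.43. The overstatement is 0.45 to 1.63 points (13% in three rows, 19% in the 100% row). This rests only on figures printed in the documents and on counts rounded down, and the two rows that need no rounding show it without that assumption. The error is conservative and alters no planned analysis, so this is a correction of a stated figure, not a flaw in the design or the analysis.

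The missing update after the early stop is secondary. SAP 5 discloses the stop but does not quantify it, and no shortfall below 150 evaluable is shown. For overall immunogenicity the two matters partly offset each other, since the printed widths remain an upper bound at 95% down to about 127 evaluable.

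**What to change.** **Main change.** Replace the values in SAP 3.2 with 12.14, 10.25, 7.91 and 2.43, state that responder counts are rounded down (or whichever rule is chosen), and record the same correction for protocol 9.5.

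**Optional.** Add a few lines to SAP 3.2:
- say that the n = 150 precision and the 2% adverse event statement refer to the original plan;
- give the attained numbers overall and by priming vaccine;
- say plainly whether the minimum of 30 evaluable was met;
- if the figures are restated, use evaluable counts for immunogenicity widths and SafAS counts for adverse event detection.

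**Cost.** One recalculated table and, if the option is taken, a few lines of text. No new participants are needed and no analysis changes.

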3.3 Populations for Analyses

The following populations are defined:

Participant Analysis Set	Description
	Participants who have received the study vaccine. All participants will have their safety analyzed according to the vaccine they actually received. Safety data recorded for a vaccine received out of the protocol design will be excluded from the analysis (and listed separately).
Full analysis set (FAS)	Subset of SafAS.

	Participants who received the study vaccine and had a valid post-vaccination serology result. Participants will be analyzed according to the intervention they received.
Per-protocol analysis set (PPAS)	Subset of FAS.
	Participants presenting with at least 1 of the following relevant protocol deviations will be excluded from the PPAS:
	 Participant did not meet all protocol-specified inclusion criteria/exclusion criteria
	Participant did not receive the study vaccine
	 Preparation and/or administration of vaccine was not done as per-protocol
	 Participant did not provide a post-dose serology sample in the proper time window or a post-dose serology sample was not drawn (Blood sampling 2 (BL0002) / Visit 2: Visit 1+ 30 day (+14 days))
	 Participant's post-dose serology sample did not produce a valid test result (i.e., results for all meningococcal antigens are missing)
	 Participant had other protocol violations that affected the participant's immune response, as determined by the clinical team before locking the database
	 Participant received a protocol-prohibited Category 2 or Category 3 therapy/medication/vaccine

3.4 Statistical Analyses

3.4.1 General Considerations

Immunogenicity parameters will be analyzed in specified analysis sets (PPAS and FAS) in the overall population, as well as by primed vaccine groups. Safety analysis will be performed on the SafAS.

The statistical analyses will be performed under the responsibility of the Sponsor's Biostatistics platform using SAS® Version 9.4 or later.

For descriptive purposes, the following statistics will be presented:

Table 3.1: Descriptive statistics produced

Disposition and follow-	Categorical data	Number of participants.		
up description		Percentage of participants.		
	Continuous data	Mean, standard deviation, quartiles, minimum and		
		maximum.		
Baseline characteristics	Categorical data	Number of participants.		
		Percentage of participants.		
	Continuous data	Mean, standard deviation, quartiles, minimum and		
		maximum.		
Clinical safety results	Categorical data	Solicited: Number and percentage (95% CIs for		
		main endpoints) of participants.		
		Unsolicited: Number and percentage (95% CIs for		
		main endpoints) of participants and number of		
		events.		
Immunogenicity	Categorical data	Number and percentage (95% CIs for main		
results	(seroprotection,	endpoints) of participants		
	seroconversion, cutoff)			
	Continuous data (titer /	Log10: Mean and standard deviation. Anti-Log10		
	data†)	(work on Log10 distribution, and anti-Log10		
		applied): Geometric mean, 95% CI of the geometric		
		mean, quartiles, minimum, and maximum. Graphical		
		representation by Reverse Cumulative Distribution		
		Curve (RCDC).		

The confidence interval (CI) for the single proportion will be calculated using the exact binomial method (Clopper-Pearson method, quoted by Newcombe (1), i.e., using the inverse of the beta integral with SAS®.

For immunogenicity results, assuming that Log10 transformation of the titers / data follows a normal distribution, at first, the mean and the 95% CI will be calculated on Log10 (titers / data) using the usual calculation for normal distribution (using Student's t distribution with n-1 degree of freedom), then antilog transformations will be applied to the results of calculations, in order to provide geometric means (GMs) and their 95% CI.

3.4.2 Immunogenicity Endpoints

Descriptive statistics will be provided for the hSBA and rSBA antibody titers against meningococcal serogroups (A, C, W, and Y) and for antibody concentrations against tetanus toxoid contained in MenQuadfi[®] as a carrier protein.

All immunogenicity analyses will be performed on the PPAS and FAS.

In general, categorical variables will be summarized and presented by frequency counts, proportion percentages, and CIs. The 95% CIs of point estimates will be calculated using the normal approximation for quantitative data and the Exact binomial distribution (Clopper-Pearson method) for percentages. For GMTs, 95% CIs of point estimates will be calculated using normal approximation assuming they are log-normally distributed.

For immunogenicity data, assuming that log10 transformation of the titers / concentrations follows a normal distribution, first, the mean and 95% CIs will be calculated on log10 (titers / concentrations) using the usual calculation for normal distribution, then antilog transformations will be applied to the results of calculations, to compute GMTs / GMCs and their 95% CIs.

Reverse cumulative distribution curve (RCDC) figures will be provided for the antibody titers against meningococcal serogroups and the antibody concentrations against tetanus toxoid contained in MenQuadfi[®].

In summary, descriptive analyses on A, C, Y, and W serogroups on D01 and D31 after vaccination with MenACYW conjugate vaccine will include but not be limited to:

- hSBA and rSBA seroprotection rate (titer ≥ 1:8) and 95% CI
- hSBA and rSBA GMTs and 95% CI
- hSBA and rSBA titer distribution and RCDC
- Percentage of participants with hSBA titer ≥ 1:4 and 95% CI
- Percentage of participants with rSBA titer ≥ 1:128 and 95% CI
- Percentage of participants with hSBA and rSBA titer ≥4-fold rise from pre-vaccination to post-vaccination, and 95% CI
- Percentage of participants with hSBA and rSBA vaccine seroresponse rate and 95% CI hSBA vaccine seroresponse for serogroups A, C, Y, and W defined as:
 - o For a participant with a pre-vaccination titer < 1:8, the post-vaccination titer must be $\geq 1:16$
 - \circ For a participant with a pre-vaccination titer $\geq 1:8$, the post-vaccination titer must be at least 4-fold greater than the pre-vaccination titer

rSBA vaccine seroresponse defined as:

- o a post-vaccination rSBA titer ≥ 1:32 for participants with pre-vaccination rSBA titer < 1:8, or
- o a post-vaccination titer ≥ 4 times the pre-vaccination titer for participants with pre-vaccination rSBA titer ≥ 1.8

In addition, descriptive analyses on anti-tetanus antibody concentrations will include but not be limited to:

- GMCs and 95% CI
- The percentage of participants with antibody concentrations to tetanus toxoid ≥ 0.01 international units (IU)/mL, ≥ 0.1 IU/mL and ≥ 1.0 IU/mL and 95% CI

3.4.3 Safety Endpoints

Safety analyses will be performed on the SafAS and presented overall. The main parameters for the safety endpoints will be described by 95% CIs using the Exact binomial method (Clopper-Pearson method).

The safety analysis that will be presented by priming vaccines status for the following safety summary tables:

- Safety overview after MenACYW conjugate vaccine dose received at V01,
- Summary of unsolicited AEs within 30 days after MenACYW conjugate vaccine dose received at V01
- Overview of SAEs.

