1 PROTOCOL SUMMARY

1.1 SYNOPSIS

Protocol Title:

A descriptive, Phase IV, open-label, single-arm multi-center study to assess the immunogenicity and safety of MenQuadfi[®] as a booster vaccine in healthy toddlers 12 to 23 months of age who had been primed with at least 1 dose of another quadrivalent meningococcal conjugate vaccine, ie, Nimenrix[®] (MCV4-TT) or Menveo[®] (MCV4-CRM), in infancy.

Brief Title:

Study of immunogenicity and safety of MenQuadfi® as a booster vaccine in healthy toddlers 12 to 23 months, regardless of the quadrivalent meningococcal conjugate vaccine used for priming in infancy.

Rationale:

The objective of MEQ00086 study is to describe the immunogenicity and safety of MenQuadfi[®] (Meningococcal Polysaccharide [Serogroups A, C, Y, and W] Tetanus Toxoid (TT) Conjugate Vaccine, also identified as MenACYW conjugate vaccine or as MenACYW-TT) when administered as a booster dose in healthy toddlers 12 – 23 months of age who had been primed during the first year of life with at least 1 dose of another licensed quadrivalent meningococcal conjugate vaccine, either Nimenrix[®] (MCV4-TT) or Menveo[®] (MCV4 - CRM). The evidence generated from this study will provide reassurance that MenQuadfi[®] used as a booster dose in toddlers who had been primed with another licensed MCV4 vaccine will provide an adequate immune response and protection against invasive meningococcal disease (IMD).

Objectives, Endpoints:

Objectives	Endpoints
Immunogenicity	Immunogenicity
1) To describe the immune response to a booster dose of MenQuadfi® as measured by the serum bactericidal assay using human complement (hSBA) in toddlers aged 12-23 months, who had been primed with at least 1 dose of another MCV4 vaccine during	 hSBA antibody titers ≥ 1:8 (seroprotection) against meningococcal serogroups A, C, W and Y at D31 (+14 days) after booster vaccination with MenQuadfi® At Day (D)01 (baseline) before vaccination and at D31 [+14 days] after the
infancyTo describe the antibody responses to meningococcal serogroups A, C, W, and Y	administration of a booster dose of MenQuadfi® the following will be assessed for meningococcal serogroups A, C, W and Y
before and 1 month after a booster dose of	as measured by hSBA:

- MenQuadfi® as measured by hSBA and rSBA in toddlers 12-23 months of age who had been primed with at least 1 dose of another MCV4 vaccine during infancy

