• Route of administration: Intramuscular (IM) injection

Statistical Considerations:

All analyses will be descriptive; no hypotheses will be tested.

In general, categorical variables will be summarized and presented by frequency counts, proportion percentages, and CIs. The 95% CIs of point estimates will be calculated using the normal approximation for quantitative data and the Exact binomial distribution (Clopper-Pearson method) for percentages. For geometric mean titers (GMTs), 95% CIs of point estimates will be calculated using normal approximation assuming they are log-normally distributed.

^{*}Tetanus toxoid protein quantity is approximate and dependent on the polysaccharide-to-protein ratio for the conjugates used in each formulation

For immunogenicity data, assuming that log10 transformation of the titers / concentrations follows a normal distribution, first, the mean and 95% confidence intervals (CIs) will be calculated on log10 (titers / concentrations) using the usual calculation for normal distribution, then antilog transformations will be applied to the results of calculations, to compute geometric mean titers / concentrations (GMTs / GMCs) and their 95% CIs.

All immunogenicity analyses will be performed on the Per-Protocol Analysis Set (PPAS) and presented overall and by priming vaccine. Additional immunogenicity analyses will be performed on the full analysis set (FAS). Descriptive statistics will be provided for the hSBA and rSBA antibody titers against meningococcal serogroups (A, C, W, and Y) and for antibody concentrations against tetanus toxoid contained in MenACYW conjugate vaccine as a carrier protein.

Safety analyses will be performed on the Safety Analysis Set (SafAS) and presented overall and by priming vaccine. The main parameters for the safety endpoints will be described by 95% CIs using the Exact binomial method (Clopper-Pearson method).

[figure not shown]
Data Monitoring/Other Committee:

No

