9 STATISTICAL CONSIDERATIONS

Clinical data will be analyzed under the responsibility of the Biostatistics Platform of the Sponsor.

A statistical analysis plan (SAP) will be written and peer reviewed before any analyses. In accordance with the protocol, the SAP will describe all analyses to be performed by the Sponsor and all the conventions to be taken.

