9.3.3 Safety Endpoints

Safety

Safety analyses will be performed on the SafAS and presented overall and by priming vaccine. The main parameters for the safety endpoints will be described by 95% CIs using the Exact binomial method (Clopper-Pearson method).

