4.2.2.5 Adverse Events Leading to Study Discontinuation

This information will be summarized as collected. A flag is available in the clinical database for all AEs in order to identify AEs leading to discontinuation before the end of active phase. In general, the items that are counted are:

- Disposition table: A participant who, on the "Completion at End of Study" form question "What was the participant's status?" has "Adverse Event" checked.
- Safety overview table: A participant who has either on the "Completion at End of Study" form, question "What was the participant's status?" has "Adverse Event" checked or lists a solicited AE that has "Caused Study Termination" checked that is at least Grade 1 or an unsolicited AE that has "Caused Study Discontinuation" checked that is at least Grade 1 or missing and is within the time period indicated.
- System Organ Class (SOC)/Preferred Term (PT) table: A solicited AE that has "Caused Study Termination" checked that is at least Grade 1 or an unsolicited AE that has "Caused Study Discontinuation" checked that is at least Grade 1 or missing and is within the time period indicated.

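### SAP 3.4.3 splits only three safety tables by priming vaccine, none of them a solicited-reaction table, although the protocol sets no such limit and SAP Section 5 records no change

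*SAP*

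**What the plan says.** The protocol makes the same commitment twice. Protocol 9.3.3 reads "Safety analyses will be performed on the SafAS and presented overall and by priming vaccine", and the synopsis (Protocol 1.1, Statistical Considerations) reads "Safety analyses will be performed on the Safety Analysis Set (SafAS) and presented overall and by priming vaccine". Neither names tables or limits the split. Protocol 9 ties the SAP to this: "In accordance with the protocol, the SAP will describe all analyses to be performed by the Sponsor".

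SAP 3.4.3 repeats the Protocol 9.3.3 sentence but stops at the overall presentation. The priming split follows separately: "The safety analysis that will be presented by priming vaccines status for the following safety summary tables". Three tables come after it: the safety overview, the summary of unsolicited AEs within 30 days, and the overview of SAEs.

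For immunogenicity, SAP 3.4.1 plans results "in the overall population, as well as by primed vaccine groups", with no list of tables. On safety, the same section names only the SafAS as the analysis set.

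SAP Section 5 (changes in conduct or planned analyses) covers four matters: the dropped analysis by number of priming doses, the early end of recruitment, the unused COVID form, and the rule for the highest temperature. The by-priming safety tables are not among them.

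**The concern.** The brief title presents the booster as given "regardless of the quadrivalent meningococcal conjugate vaccine used for priming in infancy". How toddlers primed with each vaccine tolerate it is part of that description, and solicited reactions are its most detailed component. The SAP derives presence, intensity, time of onset, days of presence and ongoing status for them. If the SAP list is followed, those results appear only for the two priming groups combined. A reader cannot tell whether this was decided or overlooked. The same priming groups are also handled differently for immunogenicity and for safety, and no reason is given.

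**Working it through.** The plan gives no figure on this point, so the check is mainly a comparison of text. The interval calculations at the end only illustrate precision.

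**1. Which endpoints have a by-priming table?** The endpoints come from Protocol Table 3.1 and SAP Table 2.1, and the tables from SAP 3.4.3.

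| Safety endpoint | By-priming table in SAP 3.4.3 |
|---|---|
| Immediate unsolicited systemic AEs (30 min) | No table of its own; these are unsolicited AEs, so they fall within the unsolicited-AE table |
| Solicited injection-site reactions (7 days) | None listed |
| Solicited systemic reactions (7 days) | None listed |
| Unsolicited AEs (30 days) | Yes |
| SAEs, including AESIs | Yes (overview) |

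Protocol 10.2.2 defines an unsolicited AE as one that does not meet the solicited conditions, so the unsolicited-AE table cannot contain solicited reactions. The two uncovered endpoints comprise 3 injection-site terms (tenderness, erythema, swelling) and 6 systemic terms (fever, vomiting, abnormal crying, drowsiness, appetite lost, irritability), from SAP Tables 4.1 and 4.2: 3 + 6 = 9.

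**2. Is the list a restriction or a set of examples?** Two features point to a restriction. The preceding sentence in SAP 3.4.3 omits the by-priming phrase that Protocol 9.3.3 has. SAP 3.4.2 marks its lists as non-exhaustive, and SAP 3.4.3 does not.

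**3. Does another part of the SAP restore the split?** None does. SAP 4.2.2.5 shows that the safety overview draws on solicited data for one item, study discontinuation: it counts a participant whose end-of-study form has Adverse Event "checked or lists a solicited AE that has" the study-termination box marked. No other solicited row is specified.

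**4. Could small numbers be the reason?** Section 5 says "the recruitment had to be stopped before reaching 180 subjects in total (and minimum of 30 evaluable participants enrolling of the 2 priming vaccines", but it does not connect this to the safety tables and gives no group sizes. To show precision, assume 10, 20 or 29 participants in the smaller group. The 30 minimum refers to evaluable participants, so the SafAS count could be higher. The exact (Clopper-Pearson) limits for x events in n are:

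- lower = the 0.025 quantile of Beta(x, n − x + 1)
- upper = the 0.975 quantile of Beta(x + 1, n − x)
- upper for x = 0: 1 − 0.025^(1/n)

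| Events/n | 95% CI | Width (points) | Upper limit at 0 events |
|---|---|---|---|
| 3/10 | 6.7–65.2% | 58.6 | 30.8% |
| 6/20 | 11.9–54.3% | 42.4 | 16.8% |
| 9/29 | 15.3–50.8% | 35.5 | 11.9% |
| 45/150 (comparison) | 22.8–38.0% | 15.2 | not shown |

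Widths use unrounded limits. The event counts are chosen to show precision near 30% and at zero; they are not expected rates. Frequent reactions could be described roughly, while Grade 3 results would be weak.

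**The case against.** The strongest reply is that Protocol 9.3 calls itself a summary and leaves technical detail to the SAP. The SAP still presents some safety results by priming vaccine and merely says which tables carry the split. However, specifying detail is different from narrowing a stated presentation, and the wording of SAP 3.4.3 reads as narrowing.

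A second point stands in part. The content of the safety overview is unknown, and it may hold rows for any solicited reaction or for Grade 3. What can be shown is that the tables by term are unlisted, not that every solicited result by priming vaccine is lost.

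Third, Section 5 is not a complete log. SAP 3.4.2 adds a tetanus threshold of 1.0 IU/mL that Protocol 9.3.2 does not have, and Section 5 does not list it. This is fair, and its silence is no sign of concealment. Yet an added threshold removes nothing, and Section 5 does record the comparable removal of results by number of priming doses.

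Fourth, the assumed group sizes and event counts do not measure the defect, and the wide intervals limit what the extra tables would show. Both statements are correct. They could support a stated decision to omit the tables. They do not explain why immunogenicity keeps its split, or why the SAE overview keeps one, when the protocol describes solicited reactions as common and expected and therefore easier to describe in a small group.

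Finally, the consequences are limited. No hypothesis is tested, the safety objective is not divided by priming vaccine, and all five endpoints are reported overall. This stands and bounds the importance of the point.

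**Conclusion.** The concern holds. The SAP narrows the by-priming safety presentation relative to the protocol, gives no reason, and does not record the change. Two of the five safety endpoints, covering nine solicited terms, have no listed by-priming table. This rests on reading the SAP 3.4.3 list as exhaustive, which its wording supports but does not say outright. The amount of information lost depends on the unspecified rows of the safety overview. The impact is modest and confined to descriptive reporting, so the change should be made, but no main result of the study depends on it.

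**What to change.** Preferred: add the solicited injection-site and solicited systemic reaction tables to the by-priming list in SAP 3.4.3, with Clopper-Pearson 95% CIs for the main parameters. Any grade and Grade 3 by term would be a reasonable choice; that level of detail is a suggestion, as the protocol does not set it. The cost is a few more table shells from data already collected and derived for the SafAS, with wide intervals in the smaller group.

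If the reduction is intended, for example because recruitment ended early, state it and its reason in SAP Section 5 and specify which solicited rows the by-priming safety overview contains. This takes one or two sentences, but it only documents the departure: detailed solicited results by priming vaccine would remain unreported.
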